Study Design	This will be a single site, phase 2, safety and tolerability trial of 4'-phosphopantetheine (4'-PPT), a downstream product of intermediary metabolism in children and adults with pantothenate kinase-associated neurodegeneration (PKAN), an inborn error of vitamin B5 metabolism. There will be two cohorts: For the “ Primary Cohort ”, an initial 6-month, dose-ranging, parallel-group, randomized, double-blind, placebo-controlled phase will be followed by an 18-month, single-dose, open-label phase. During the double-blind phase, participants will be randomly assigned to receive one of three doses (5mg/m ² or 15mg/m ² or 20mg/m ²) or placebo in a 1:1:1:1 distribution. All participants will be assigned to a single dose (15mg/m ²) during the subsequent open-label phase. The primary data analysis will be based on the Primary Cohort dataset. Once the target enrollment of the Primary Cohort is met in the double-blind arm, new participants entering the study will be enrolled directly into an open-label arm that will last until the final subject in the Primary Cohort has completed their participation, including up to 4 additional mos for screening and follow-up. This will be designated the “ Open-label Cohort ”. Because the rolling enrollment into the Open-label Cohort will result in variable duration of participation, the safety and biomarker data from

	
the Open-label Cohort will not be used for the primary data analysis, although a secondary analysis of these data may be used for regulatory filings.
 
The study product will be taken once daily but may be split into divided doses if the participant does not tolerate a single daily dose.
 
Note that the double-blind phase of the study is not intended to be dose-finding: all doses are predicted to be many-fold below toxicity and all doses are predicted to correct the metabolic defect in PKAN, albeit with slightly differing time courses. The range of doses to be used during the double-blind phase is employed purely to test our hypotheses regarding the pharmacodynamic profile of an exploratory 'proof of concept' biomarker, CoASY. The mid-dose of 15mg/m² is based on the minimum effective dose in the mouse and converted to the human equivalent dose using an FDA algorithm and other guidances.

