Number of Participants	
Approximately 64 participants (allowing for 4 dropouts to provide 60 evaluable participants) in the Primary Cohort; up to 86 additional participants in the Open-label Cohort.
 
Participant recruitment will not be limited by PKAN phenotype but participants will be stratified to ensure approximately equal distribution of 'classic' and 'atypical' participants in each group. We anticipate about half of the participants will have classic disease.
 
Classic participants are defined as onset motor sx before age 5 and (if over 10 at enrollment) loss of independent ambulation by age 10. Goal is n=30 classic participants.Atypical participants are defined as all other PKAN participants who don't meet classic disease criteria. Goal is n=30 atypical participants.
Main Eligibility Criteria	
Inclusion Criteria
 
To be included in this trial, participants must:
 
Have a diagnosis of PKAN confirmed by: a) genetic testing confirming 2 pathogenic or likely pathogenic mutations, or (b) typical findings on exam and brain MR imaging with only one pathogenic mutation +/- a second likely pathogenic or Variant Of Uncertain Significance (VOUS) in PANK2, or (c) typical findings on exam and brain MR imaging with a single likely pathogenic or VOUS in PANK2, or (d) be a symptomatic sibling of a proband subject meeting a, b, or c.Be between age 3 months and age 89 years at the time of screening.Be able to take the study product by mouth or via gastrostomy tube.Be willing and able to complete study procedures / telephone visits / blood draws independently, OR have a caregiver / parent willing and able to assist with these tasks.Be enrolled or willing to enroll in the PKANready natural history study (eIRB 10832)Be resident in North America for the duration of the trial. 
Exclusion Criteria
 
To be included in this trial, participants must NOT:

eIRB 18782 CoA-Z in PKAN (NIH)

	
 • Have had exposure to a putative PANK2 'bypass' therapeutic agent in the 30 days prior to screening. • Be concurrently enrolled in another interventional clinical trial. • Have concurrent medical or other conditions expected to preclude completion of study procedures or confound the assessment of clinical and laboratory measures of safety.

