Primary Outcome	
Our primary endpoints are:
 
 • Safety outcome measures will include treatment-emergent adverse events and abnormalities on standard laboratory tests. TEAE will be collected at 10 time points over 24 months of treatment in the Primary Cohort and collected at up to 7 time points over up to 18 months of treatment in the Open-label Cohort. Laboratory tests will be collected at 9 time points in the Primary Cohort and up to 6 time points in the Open-Label Cohort over the same respective periods. • Tolerability outcomes will be assessed via participant retention in the study and adherence to the study product regimen.
Secondary Outcomes	
Our secondary endpoint is: CoASY mRNA expression levels measured at 8 time points in the Primary Cohort and at up to 6 time points in the the Open-label Cohort.

Safety Assessments	
Treatment-emergent Adverse Events Baseline and at intervals throughout treatment (10 time points for the Primary Cohort and up to 7 timepoints for the Open-label Cohort)
 
 • Treatment-emergent adverse events will be classified according to Medical Dictionary for Regulatory Activities (MedDRA) terminology. • Severity of the AEs will be graded according to the NCI Common Terminology Criteria for Adverse Events, Version 4.0 
Clinical safety laboratory studies Baseline and at intervals throughout treatment (9 time points for Primary Cohort; up to 6 time points for the Open-label Cohort)
 
 • Complete metabolic profile (Includes Na^+, K^+, Cl^-, CO_2, BUN, Creat, Ca^{2+}, Glu, Alb, T. Protein, Alk Phos, T. Bili, AST, ALT) • Complete blood count with auto-differential • Creatine kinase (CK)
Tolerability Assessments	
Participant retention
 
 • During treatment and follow up • Number of participants retained in each arm at each of the follow up time points 
Participant adherence to study product regimen as measure of tolerability
 
 • During treatment and follow up • Mean percent of study product consumed

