Sample Size Considerations	
Because PKAN is an ultra-rare disease, we are limited to 64 participants for the Primary Cohort (15 in each arm + 4 potential dropouts allowing for 5% loss to follow-up) whom we will recruit from our established research registry, (prioritizing those participating in our “PKANready” ongoing natural history study) as well as by methods described within the protocol. When our double-blind enrollment goal is met, enrollment of up to 86 additional participants will shift to an open-label arm, designated the Open-label Cohort. Our primary objective is to estimate effects of the study product and we will prioritize effect sizes over statistical power in interpreting results. Still, we wish to include sufficient numbers to estimate effects in our secondary and exploratory analyses of CoASY mRNA expression levels with some precision. In preliminary cross-sectional data, we found that the mean CoASY delta Ct (dCt) measures were 1.4 standard deviations higher in classic PKAN children (n=8) than age-matched healthy controls (n=6) on the log₂ scale, where higher dCt indicates lower CoASY activity (mean=17.39 vs 16.85, SD=0.39). We anticipate that participants at all three dose levels will resemble healthy controls after 3±2 days, while the placebo group will show no change. We simulated this change from baseline for 12 participants per group. For the standard deviation, we performed one set of simulations using the upper limit of the 60% CI for the standard deviation (0.34-0.48) as a conservative estimate. We regressed the dCt value on four indicator variables for study arm after treatment, with the intercept representing the common mean baseline value, and included a random intercept to induce correlation between paired measurements. We then used a Wald test for $\beta_{\text{placebo}1} - (\beta_{\text{low}1} + \beta_{\text{mid}1} + \beta_{\text{high}1})/3 = 0$ at $\alpha=0.05$. Pooling over 1000 simulated datasets, we find that we reject the null in 85-95% of simulations, approximating power to detect this difference at one month between the active and placebo groups.

-----------------------------------	---

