Statistical Methods	
A modified Intention-to-Treat (ITT) analysis dataset of all randomized participants who consumed at least one dose of the study product. This is also the Safety Analysis dataset.
 
The Per-Protocol dataset will include participants who consume at least 75% of assigned study product.
 
General approach
 
The proposed study takes place over 28 months in the Primary Cohort. A screening period of up to 2 months will be followed by an initial 6-month double-blind, placebo-controlled parallel trial of the study product during which participants will be assigned to one of three dose groups [5mg/m², 15mg/m², 20mg/m²]; and then by a further 18 months of open label study during which all participants will be assigned a 15mg/m² dose. Participants will be followed for up to two months beyond the end of the open-label period. The primary data analysis will be based on the Primary Cohort dataset.
 
Once the target enrollment in the Primary Cohort is met, we will shift to direct enrollment into an Open-label Cohort. A screening period of up to 2 months will be followed by up to 18 months during which all participants will be assigned a 15mg/m²

----------------------------	--

dose and follow a similar pattern of procedures as the Primary Cohort during the open-label phase of the study. Participants will be followed for up to two months beyond the end of their open-label period. Because the rolling enrollment into the Open-label Cohort will result in variable duration of participation, the safety and biomarker data from the Open-label Cohort will not be used for the primary data analysis, although a secondary analysis of these data may be used for regulatory filings.

Descriptive statistics will be presented as counts and percentages for categorical variables, counts and ranges for events, and means with standard deviations, medians, and ranges for continuous variables. For safety and tolerability measures, we will consider clinical, rather than statistical, significance. Initial determinations will be made by the independent medical safety monitor physician familiar with the study population and blinded to treatment allocation.

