For modeling and inferential tests, we will consider a p-value less than 0.1 to be significant if the magnitude and precision of the estimated effect support that conclusion. Covariates will be specified in the description below. We will perform extensive exploratory data analysis and checks of model fit and will transform variables with obvious departures from normality.

Analysis of primary endpoints

Safety Analysis

Comparisons of participants experiencing treatment-emergent adverse events and clinically-significant abnormalities on clinical labs will be reviewed for clinical significance in the Safety Analysis dataset, which includes all participants who consume at least one dose of the study product. Events expected as part of the usual disease course in PKAN, whether present at trial enrollment or not, will not be considered or captured as adverse events.

Frequencies of participants experiencing at least one adverse event (AE) will be displayed by body system and preferred term according to *Medical Dictionary for Regulatory Activities* (MedDRA) terminology. Detailed information collected for each AE will include a description of the event; duration; whether the AE meets criteria as a Serious Adverse Event (SAE); severity / grade of the event; relationship to study product; changes made to the study product in response to the AE /SAE; and clinical outcome. Severity of the AEs will be graded according to the NCI *Common Terminology Criteria for Adverse Events*, Version 4.0. If the event meets criteria as an SAE, the nature of the SAE will be classified using standard FDA criteria.

The number and percentage of patients who experienced any serious AE (SAE), treatment-emergent AE, and treatment-emergent SAE will be summarized, as well as the total number of events per arm. AE data will be presented for months 0-6 and 7-37 and cumulatively, as appropriate. Emphasis in the analyses will be placed on AEs classified as treatment-emergent.

Clinically-significant abnormalities on clinical labs will be tabulated similarly to AEs. The number and percentage of patients experiencing clinically-significant abnormalities will be compiled in summary tables to examine the distribution by collection month [0-1-3-6-7-9-12-18-24 (25) months for the Primary Cohort; and 0-1-3-6-12-18 (19) months for the Open-label Cohort].

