Note that the double-blind phase of this study is not intended to be dose-finding: all doses are predicted to be many-fold below toxicity and all doses are predicted to correct the metabolic defect in PKAN, albeit with slightly differing time courses. The range of doses to be used during the double-blind phase is employed to test our hypotheses regarding the pharmacodynamic profile of an exploratory biomarker, CoASY. The mid-dose of 15mg/m² that will be given to all participants during the open-label phase is based on the minimum effective dose in the mouse and converted to the human equivalent dose using an FDA algorithm and other guidances^[13,14]. The actual single daily dose in mL to be taken by the study participant will be calculated by the research pharmacist based on the participant's body surface area. If a subject has difficulty taking the volume of the single dose, then at the Principal Investigator's discretion the dose may be divided into 2 equal volumes and taken twice a day.

7. Study Population

a. Number of Subjects

We will screen up to 150 individuals with the goal of enrolling 64 participants, to achieve 60 participants completing the double-blind arm of the study as the Primary Cohort. We are conservatively allowing for 4 dropouts (5% loss) based on our experience in one other interventional clinical trial with this clinical population; however, if participant loss is higher than anticipated during the projected 24 month recruitment phase, we will strive to replace all dropouts to maximize our chances of achieving 60 participants completing the study. Once enrollment into the Primary Cohort is met, we will shift to enrolling up to 86 additional participants in the direct to open-label arm (Open-label Cohort).

Classic PKAN participants are defined as those with onset of motor symptoms before age 5 and (if over 10 at enrollment) loss of independent ambulation by age 10. Goal is n=30 classic participants.

Atypical PKAN participants are defined as all other PKAN participants who don't meet classic disease criteria. Goal is n=30 atypical participants.

b. Inclusion and Exclusion Criteria

For inclusion in this trial, subjects must:

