Comparisons of participants experiencing treatment-emergent adverse events and abnormalities on clinical labs will be reviewed for clinical significance in the Safety Analysis dataset, which includes all participants in the primary cohort who consume at least one dose of the study product. Events expected as part of the usual disease course in PKAN, whether present at trial enrollment or not, will not be considered or captured as adverse events.

Frequencies of participants experiencing at least one adverse event (AE) will be displayed by body system and preferred term according to *Medical Dictionary for Regulatory Activities* (MedDRA) terminology. Detailed information collected for each AE will include a description of the event; duration; whether the AE meets criteria as a Serious Adverse Event (SAE); severity / grade of the event; relationship to study product; changes made to the study product in response to the event; and clinical outcome. Severity of the AEs will be graded according to the NCI *Common Terminology Criteria for Adverse Events*, Version 4.0^[15]. If the event meets criteria as an SAE, the nature of the SAE will be classified according to standard FDA criteria.

The number and percentage of patients who experienced any serious AE (SAE), treatment-emergent AE, and treatment-emergent SAE will be summarized, as well as the total number of events per arm. AE data will be presented for months 0-6, 7-25 and cumulatively, as appropriate. Emphasis in the analyses will be placed on AEs classified as treatment-emergent.

Clinically-significant abnormalities on clinical labs will be tabulated similarly to AEs. The number and percentage of patients experiencing clinically-significant abnormalities will be compiled in summary tables to examine the distribution by collection month [0-1-3-6-7-9-12-18-24 +/- 25 months for the Primary Cohort; and 0-1-3-6-9-12-18 +/- 19 for the Open-label Cohort].

Graphic displays may be provided to illustrate the results over time. Initial review of group differences and determination of clinical significance will be performed by an unaffiliated physician familiar with the study population and blinded to treatment arm.

Tolerability Analysis

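### Open-label Cohort adverse events are listed as a primary safety endpoint but kept out of the primary analysis; the three Safety set definitions conflict, and no exposure-adjusted summary is planned for the long-term aim

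*Combined protocol and SAP*

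**What the plan says.** The synopsis, under Primary Outcome, names adverse events and laboratory abnormalities from both cohorts as primary safety endpoints. For the second cohort, treatment-emergent events are "collected at up to 7 time points over up to 18 months of treatment in the Open-label Cohort". The synopsis, under Study Design and again under Statistical Methods (General approach), then says that "the safety and biomarker data from the Open-label Cohort will not be used for the primary data analysis". The one reason offered is that rolling entry makes time in the study unequal. Both places add that a secondary analysis may serve regulatory filings.

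The Safety Analysis dataset is defined three times:

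- Synopsis, Statistical Methods, opening lines: the modified intention-to-treat set (randomised people who took any product) doubles as the safety set. Open-label Cohort members are never randomised, so they are out.
- Synopsis, Safety Analysis: "Safety Analysis dataset, which includes all participants who consume at least one dose of the study product". There is no limit by cohort, so they are in.
- Section 10.b, Safety Analysis: "Safety Analysis dataset, which includes all participants in the primary cohort who consume at least one dose of the study product". They are out.

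The same safety and tolerability sections plan laboratory-abnormality tables by month, and retention counts, for both cohorts. Adverse events are to be summarised as numbers, percentages and total events per arm. The reporting periods are months 0–6 and then 7–25 (section 10.b) or 7–37 (synopsis).

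**The concern.** Variable follow-up is a reason to report events against time at risk. It is not by itself a reason to set a cohort aside. Unequal exposure already exists inside the Primary Cohort: by the synopsis's own account, active treatment lasts 18 months in the former placebo group and 24 months in the others. Yet no exposure-adjusted rate is planned for either cohort.

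The second primary aim, to describe longer-term safety, does not depend on randomisation. Open-label Cohort participants take the same assigned dose as the Primary Cohort's open-label phase and have similar adverse event and laboratory schedules. Section 13.a says the product has not been studied in humans before, and eligibility starts at 3 months of age. How many people are observed on product therefore largely decides which harms the trial can see or exclude.

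There is also a practical problem. A programmer cannot follow all three Safety set definitions. Section 10.b restricts the set to the Primary Cohort and then asks for Open-label Cohort laboratory tables in the same section.

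**Working it through.** **Inputs**

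- Primary Cohort size (synopsis, Sample Size Considerations): "we are limited to 64 participants for the Primary Cohort (15 in each arm + 4 potential dropouts allowing for 5% loss to follow-up".
- Second cohort (synopsis, Number of Participants): "up to 86 additional participants in the Open-label Cohort".
- Allocation (synopsis, Study Design): "placebo in a 1:1:1:1 distribution", so 64 splits into 48 active and 16 placebo.
- Active treatment in the Primary Cohort (synopsis, Study Objective and Specific Aims): 24 months for active arms, 18 months for the placebo arm.
- Active treatment in the Open-label Cohort: up to 18 months. Section 5 instead counts screening and follow-up (up to 2 months each) within the 18, which could leave 18 − 4 = 14 months on product.
- Screening (section 7.a): "We will screen up to 150 individuals with the goal of enrolling 64 participants".

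**The plan's own figure.** 60 / (1 − 0.05) = 63.2, rounded up to 64 across four equal arms. This matches the plan.

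**Participants.** 64 + 86 = 150, and 86/150 = 57%. This is a ceiling. If the screening limit covers both cohorts, 150 dosed would require every screened person to enrol and take product.

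**Active exposure, full completion**

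- Primary Cohort: 48 × 24 + 16 × 18 = 1,440 person-months = 120 person-years.
- Open-label Cohort, maximum: 86 × 18 = 1,548 person-months = 129 person-years.
- Maximum open-label share: 1,548 / (1,440 + 1,548) = 51.8%.

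The documents give no enrolment curve, so shorter follow-up is an assumption. The uniform-entry rows start entry when the last Primary Cohort participant starts, close 24 months later, and cap time on product at 18 months. All rows keep 86 participants.

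| Assumption | Mean months | Open-label person-months | Share of active exposure |
|---|---|---|---|
| All reach 18 months | 18 | 1,548 | 51.8% |
| Uniform entry over 12 months | 16.5 | 1,419 | 49.6% |
| Uniform entry over 18 months | 14 | 1,204 | 45.5% |
| Uniform entry over 24 months | 11.25 | 967.5 | 40.2% |
| Mean of 9 months (half the maximum) | 9 | 774 | 35.0% |

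Section 5's 14-month reading gives the same 45.5%.

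**What the extra people would buy**

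- Zero-event 95% upper bound on the proportion affected, 1 − 0.05^(1/n): 4.6% at n = 64 and 2.0% at n = 150.
- Chance of at least one case of a 1-in-100 event, 1 − 0.99^n: 47% at n = 64 and 78% at n = 150.
- If only half of the 86 were dosed (n = 64 + 43 = 107): 2.8% and 66%.
- Zero-event upper bound on a rate, about 3 / person-years: 3/120 = 2.5 per 100 person-years for the Primary Cohort alone, 3/249 = 1.2 with the maximum open-label exposure, and 3/184.5 = 1.6 at a mean of 9 months (2,214 person-months).

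The participant-based figures give each person equal weight. They hold for events that arise within the shorter follow-up and overstate the gain for late-onset harms.

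**The case against.** A reader might infer that the Open-label Cohort is left out of the safety analysis altogether and its exposure discarded. The documents do not support that. The exclusion covers the primary analysis only. Laboratory and retention tables for that cohort are planned, and both are components of the primary endpoints. Section 10.d lists individual safety events without limiting them to one cohort. Section 12 has the principal investigator review every adverse event and the monitoring board review summary reports. The permissive wording about a secondary analysis attaches to its use in filings, so it does not clearly make the analysis optional.

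Keeping the randomised cohort primary is also defensible. The long-term part of the primary hypothesis compares initial dose groups, and Open-label Cohort participants have none. The aim is framed by Primary Cohort durations, and a cohort treated for at most 18 months says nothing about months 18–24.

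Nor do person-time rates dispose of unequal follow-up on their own. A single rate assumes a roughly constant hazard and can mislead when events cluster early.

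All of this stands and limits the point. It does not reconcile the three definitions, supply an adverse event table or method for the Open-label Cohort, or explain why unequal follow-up should keep that cohort out of a descriptive summary.

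**Conclusion.** The point holds in a limited form. The plan is inconsistent about whose safety data are primary, and its descriptive long-term aim would rest on about 64 participants and 120 active person-years, assuming full completion. The Open-label Cohort could add up to 86 people and at most 129 person-years. Its share of active exposure is about 52% at the ceiling and roughly 35–50% under the shorter follow-up assumed above. With all 150 dosed, the zero-event bound goes from 4.6% to 2.0%, and the chance of seeing a 1-in-100 event from 47% to 78%, for events arising within the shorter follow-up.

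It would go too far to say that the plan omits most of the people exposed: 57% is reached only if the cohort fills completely. The randomised comparisons are not affected. This is a worthwhile, inexpensive correction rather than a flaw that undermines the trial.

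**What to change.** 1. Use one definition of the Safety Analysis dataset in the synopsis (Statistical Methods opening and Safety Analysis) and section 10.b, and make Primary Outcome state which cohort serves which endpoint.
2. Keep the months 0–6 active-versus-placebo comparison, and the comparison between initial dose groups, in the Primary Cohort only.
3. For the descriptive long-term aim, pre-specify an all-active-exposure set: anyone in either cohort with at least one dose of 4'-PPT, with time counted from the first active dose (Month 6 for the former placebo group).
4. In that set, report adverse events and serious adverse events by system and term as number, percent and rate per person-year with exact intervals, by cohort and pooled. Split the rates by time on treatment, because the hazard may not be constant.

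The cost is SAP text and additional tables, since the schedules already collect adverse events and laboratory data in both cohorts. The pooled column would be non-randomised, would mix cohorts enrolled at different times, and would add nothing beyond 18 months. The by-cohort columns should therefore stand beside it.
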